5.2.10 Follow-up and Reporting of Pregnancies

We will include KPNC members who receive Flublok Quadrivalent vaccine or SD-IIV vaccine(s) while aged 18–64 years. Follow-up for outcomes based on PCR-confirmed influenza will include only the first positive PCR test (for influenza) per influenza season, and only if it is ≥ 14 days after vaccination, and follow-up will continue either through April 30 of each influenza season or until exit from KPNC, whichever occurs earlier. In the KPNC system, influenza PCR tests are used for clinical purposes, thus the “trigger” for an influenza PCR test is based on clinical presentation. The decision to test is up to each physician. KPNC also monitors the influenza season, which can affect the total amount of influenza testing at any point in the season.

Pregnancy is not an exclusion criterion for this study. Patients who are ≥ 18 years old and pregnant at the time of vaccination will be included in the analysis. Pregnant patients will be followed in the same way they normally would for routine influenza vaccination.

As described in Section 10.1, in the event that KPVSC reviews individual patient charts within the EMR and there is written notation in the medical record indicating that a health care provider attributed a serious or unexpected adverse event to Flublok Quadrivalent vaccine, KPVSC will report the adverse event possibly related to Flublok Quadrivalent vaccine.

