We will also be monitoring the balance of potential confounders that may be related to influenza and to PCR testing in order to confirm that we are achieving the balance intended by our quasi-randomized shipment of vaccines to clinics. Once vaccinations begin, we will monitor on a weekly basis the balance of Flublok vaccinees versus SD-IIV vaccinees with respect to facility, sex, and age group (18–49 years and 50–64 years). Additional demographic variables such as race and ethnicity may also be monitored. We will also monitor balance with respect to comorbidities such as chronic obstructive pulmonary disease (COPD), asthma, and diabetes (to be specified further in the SAP). If we find that any facility is using Flublok or SD-IIV more (or less) than needed to achieve balance, we will work with the influenza program manager to adjust what is being administered. If despite our efforts, there is still imbalance, we can address these imbalances at the analysis stage, adjusting for, or stratifying by, the relevant covariates.

We plan to assess the outcomes that occur ≥ 14 days after vaccination up through April 30 of each influenza season. It is possible that patients enter, exit, and re-enter the KPNC population during the study period. At the analysis stage, we will make the most appropriate determination for how to handle such cases.

For outcomes not based on PCR-confirmed influenza (e.g., hospitalized pneumonia and cardio-respiratory events), we will develop an algorithm (to be described in the Statistical Analysis Plan) to measure the intensity of influenza circulation to guide when to start and stop following for such events (e.g., as determined by the algorithm, hospitalized pneumonia during June when influenza is not circulating would not be included).

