4.2 Secondary Endpoints and Assessment Methods

For each of the secondary outcomes listed below, we will count the first event of the outcome per influenza season and censor follow-up after the first event. The influenza season is defined as the first day that KPNC begins use of the Cepheid GeneXpert PCR assay for the influenza season (generally the first Tuesday of October); the end of the season is generally determined when the proportion of influenza-positive PCR tests drops below 10%, or the first week of May, whichever is later.

For all secondary objectives excluding the sub-analyses by pre-existing conditions, adjustment for multiplicity will be applied following the Holm adjustment method¹:

1. We will rank order the 5 p-values obtained from tests of the 5 null hypotheses about rVE with respect to each of the 5 secondary outcomes listed above.
2. The 5 p-values will be ranked in order from the smallest p-value to the largest: $p_{(01)} \leq p_{(02)} \leq p_{(03)} \leq p_{(04)} \leq p_{(05)}$
3. The corresponding alpha critical values to determine significance are to be used based on rank:
 - i. $\alpha_{(C_01)} = \alpha/5 = 0.0100$
 - ii. $\alpha_{(C_02)} = \alpha/4 = 0.0125$
 - iii. $\alpha_{(C_03)} = \alpha/3 = 0.0167$
 - iv. $\alpha_{(C_04)} = \alpha/2 = 0.0250$
 - v. $\alpha_{(C_05)} = \alpha/1 = 0.0500$

The 5 hypothesis tests will be done sequentially in the order given above, until one of the p-values is found to be higher than the corresponding critical value. If the lowest p-value is below 0.01, we

will reject the corresponding null hypothesis, and proceed to the next-lowest p-value. If, and only if, both the 1st and 2nd p-values are below their corresponding critical values, we will proceed to the 3rd lowest p-value. We will test the 5 secondary hypotheses sequentially in this way, comparing the next p-value to its critical value only if all of the lower p-values were below their corresponding critical values.

[figure not shown]
Among all adults 50–64 years who receive either Flublok Quadrivalent or SD-IIV during the 2018–2019, 2019–2020, and/or 2020–2021 influenza seasons, we will estimate the rVE of Flublok Quadrivalent vaccine versus SD-IIV against the following outcomes:

- PCR-confirmed hospitalized influenza

Among adults aged 50–64 years who are vaccinated with Flublok or an SD-IIV, we plan to assess the number of adults who have a PCR-positive test during the influenza season ≥ 14 days after vaccination and are hospitalized.

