The PCR-positive test must occur either: (1) during the hospital stay, or (2) a hospitalization that begins ≤ 14 days after the PCR-positive test. Visually (where the • represents a hospitalization and the PCR-positive result occurs on Day 0):

Figure 1: Timing of PCR-positive test relative to hospitalization outcome

- Hospitalized community-acquired pneumonia (CAP)

Among adults aged 50–64 years who are vaccinated with Flublok or an SD-IIV, we plan to assess the number of adults who were hospitalized with a diagnosis of community-acquired pneumonia (CAP) regardless of whether a PCR test was done.

The hospitalization for CAP must occur during the influenza season and no later than 14 days after the last day of the influenza season, as determined by KPNC.

To identify diagnoses of CAP, we will start with preliminary list of ICD-10 codes that has been previously used by KPNC (**Table 1**). Case ascertainment of CAP may be refined using an iterative process during the data analysis stage.

- Hospitalized cardio-respiratory events combined (e.g., CAP, other lower respiratory tract infections [LRTI], acute myocardial infarction, congestive heart failure, stroke)

Among adults aged 50–64 years who are vaccinated with Flublok or an SD-IIV, we plan to assess the number of adults who were hospitalized with a diagnosis of a cardio-respiratory event regardless of whether a PCR test was done.

The hospitalization for a cardio-respiratory event must occur during the influenza season and no later than 14 days after the last day of the influenza season, as determined by KPNC. To identify diagnoses of a cardio-respiratory event, we will start with preliminary list of ICD-10 codes that has been previously used by KPNC (**Table 1**).

- All PCR-confirmed influenza A

Among adults aged 50–64 years who are vaccinated with Flublok or an SD-IIV, we plan to assess the number of adults who have influenza A as identified by a PCR-positive test ≥ 14 days after vaccination up through to the end of each influenza season, compared with those who do not have a PCR-positive test by vaccine received. To be included in the cohort for analysis, the PCR test must occur during the influenza season.

- All PCR-confirmed influenza B

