We will also be monitoring the balance of potential confounders that may be related to influenza and to PCR testing in order to confirm that we are achieving the balance intended by our quasi-randomized shipment of vaccines to clinics. Once vaccinations begin, we will monitor on a weekly basis the balance of Flublok vaccinees versus SD-IIV vaccinees with respect to facility,

sex, and age group (18–49 years and 50–64 years). Additional demographic variables such as race and ethnicity may also be monitored. We will also monitor balance with respect to comorbidities such as chronic obstructive pulmonary disease (COPD), asthma, and diabetes. If we find that any facility is using Flublok or SD-IIV more (or less) than needed to achieve balance, we will work with the influenza program manager to adjust what is being administered.

By design, inpatient facilities did not participate in the quasi-randomization of influenza vaccine administration. We will therefore exclude patients who received Flublok or SD-IIV during an inpatient stay as these may be higher risk. Facilities that used only Flublok or only SD-IIV will also be excluded from the analysis.

In preparing our dataset for analysis, we will assess the balance in several ways to determine if the imbalance is substantially more than what we would expect to see. Despite our efforts, we anticipate that there will still be imbalances. We will create a facility-specific propensity score for each vaccinee, scoring their probability of receiving Flublok versus SD-IIV as a function of covariates, including but not limited to age, sex, race, ethnicity, comorbidity scores, influenza vaccination, and prior healthcare utilization history. Our Cox regression will be adjusted for the propensity score.

For PCR-confirmed outcomes, we plan to assess the outcomes that occur ≥ 14 days after vaccination up through to the end of each influenza season (as determined by KPNC, which is generally when the proportion of influenza-positive PCR tests drops below 10%) or the first week of May, whichever is later. For outcomes that are not tied to PCR-confirmation, the outcome or diagnosis must occur on or after the first day that KPNC begins use of the Cepheid GeneXpert PCR assay for the influenza season (generally the first Tuesday of October), but must begin no later than 14 days after the last day of the influenza season, as determined by KPNC.

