It is possible that patients enter, exit, and re-enter the KPNC population during the study period. Only patients who are members at the time of vaccination will be included in the analysis in order to most accurately ascertain the vaccine received. If additional exclusions need to be made based on membership, we will make the most appropriate determination for how to handle such cases at the analysis stage, but we anticipate that this would be a very small number of patients. Missing data will not be imputed.

For outcomes not based on PCR-confirmed influenza (e.g., hospitalized pneumonia and cardio-respiratory events), we will include in the analysis all such outcomes occurring within 14 days after the last day of the influenza season (as determined by KPNC) to account for influenza that may still be circulating after the “official” end of the season.

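### Hospitalised CAP and cardio-respiratory events carry no 14-day post-vaccination condition in the SAP, and the CAP code list takes in all J10/J11 influenza codes and stays open during analysis

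*SAP*

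**What the plan says.** **Time since vaccination.** Protocol 11.1 plans to assess outcomes at least 14 "days after vaccination up through April 30 of each influenza season" and excepts no outcome type. Protocol 5.2.10 repeats the rule in a sentence confined to PCR outcomes: "Follow-up for outcomes based on PCR-confirmed influenza will include only the first positive PCR test" in a season, if at least 14 days after vaccination.

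In SAP 4.2 all three PCR-based secondaries keep the condition. Hospitalised influenza, for example, needs a positive test at least 14 "days after vaccination and are hospitalized". The other two secondaries do not. For CAP: "The hospitalization for CAP must occur during the influenza season and no later than 14 days after the last day of the influenza season". Cardio-respiratory events have the same limits. SAP 5.1.1.2 ties the 14-day rule to PCR-confirmed outcomes and then says of the rest: "For outcomes that are not tied to PCR-confirmation, the outcome or diagnosis must occur on or after the first day that KPNC begins use", meaning use of its seasonal PCR assay. It later adds that "we will include in the analysis all such outcomes occurring within 14 days after the last day of the influenza season". The non-PCR exploratory outcomes in SAP 4.3 also have calendar limits only.

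**Case definition.** Protocol 8.2.1 leaves the CAP codes to the SAP. SAP Table 1, headed as preliminary, lists J10 and J11 with all subcodes under CAP and describes them only as influenza. SAP 4.3 uses the same codes for clinically diagnosed influenza. The Table 1 row for lower respiratory infections (LRTI) imports every CAP code. SAP 4.2 adds: "Case ascertainment of CAP may be refined using an iterative process during the data analysis stage". Protocol 6.4 lists blinding as not applicable. SAP 2.2 limits both outcomes to primary diagnoses.

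**The concern.** Both outcomes are among the five secondaries tested under Holm in SAP 4.2, so each can support a formal claim. Three things weaken them.

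- The plan's own rule implies that events in the first two weeks are too early to reflect a vaccine difference. Counting them pulls rVE toward zero.
- Influenza admissions without pneumonia count as pneumonia. If the vaccines differ mainly against influenza, part of an apparent pneumonia effect is an influenza effect already tested as hospitalised influenza. This pushes the CAP rVE up.
- The definition has no stated lock in an open study, and any change to the CAP row passes into the composite through the LRTI row.

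A concrete case: an admission on day 5 after vaccination with J10 as primary diagnosis and a positive PCR is excluded from hospitalised influenza but counted as CAP.

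**Working it through.** **1. The plan's own figure.** Protocol Section 15, row 41 (age 50-64, pneumonia hospitalisation, December-March): 519,699 per arm, comparator risk 0.00248, RR 0.90, stated power 0.74. The second risk is 0.00248 x 0.90 = 0.002232 and the difference is 0.000248. The standard error is sqrt[(0.00248 x 0.99752 + 0.002232 x 0.997768)/519,699] = 0.0000951, so z = 2.608 and power = Phi(2.608 - 1.960) = 0.741. The figure reproduces. No stated figure is disputed here; 0.00248 is used below.

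**2. Share of events on days 0-13.** The documents do not give it.

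From the documents:
- First vaccination 16 September 2018 (Protocol 5.1.5, SAP 5.4).
- More than 75% vaccinated before Thanksgiving (Protocol 5.1.4).
- Season start on the first Tuesday of October, here 2 October 2018. End in the first week of May plus 14 days, taken as 21 May 2019.

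Assumed: 75% or 90% vaccinated evenly from 16 September to 22 November, the rest evenly to 31 January or 30 April; no vaccine difference on days 0-13.

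Summing in-season person-days, weighted by relative incidence:

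| Incidence outside December-March, relative to those months | Share s of events on days 0-13 |
|---|---|
| 100% (flat) | 5.9-6.8% |
| 50% | 4.2-5.3% |
| 25% | 2.9-4.2% |

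The hazard ratio over all counted events is about s x 1 + (1 - s) x HR, so observed rVE = (1 - s) x true rVE. For a true 10%: 10% x (1 - 0.068) = 9.3% and 10% x (1 - 0.029) = 9.7%.

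**3. Effect of the J10/J11 codes on CAP rVE.** Let b = 0.00248 (pneumonia base), h = risk of hospitalised influenza, f = share of those admissions without pneumonia. Assume 30% rVE against influenza, none against other pneumonia, and influenza pneumonia already inside b.

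- CAP limited to pneumonia: rVE = 0.30 x h x (1 - f)/b
- CAP with all J10/J11: rVE = 0.30 x h/(b + h x f)

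The power table gives h = 0.00120. That is 0.00120/0.00205 = 59% of its own test-positive rate for this age group, whereas Protocol 8.1.1 says only a very small portion of cases is admitted. So a second value is shown: 10% admitted (assumption), h = 0.000205.

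| h | f | Pneumonia only | All J10/J11 | Difference (points) |
|---|---|---|---|---|
| 0.00120 | 25% | 10.9% | 12.9% | 2.1 |
| 0.00120 | 50% | 7.3% | 11.7% | 4.4 |
| 0.00120 | 75% | 3.6% | 10.7% | 7.0 |
| 0.000205 | 25% | 1.9% | 2.4% | 0.6 |
| 0.000205 | 50% | 1.2% | 2.4% | 1.1 |
| 0.000205 | 75% | 0.6% | 2.3% | 1.7 |

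If 5% are admitted the difference is 0.3-0.9 points; if 20%, 1.0-3.2. Differences use unrounded values. The primary-diagnosis limit lowers h: halving 0.00120 gives 1.4-4.3 points. The documents do not say which codes defined 0.00248, and its December-March window is shorter than the SAP's.

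**The case against.** **On the lag.** Protocol 5.2.10 states the rule for PCR outcomes only, and Protocol 11.1 gives non-PCR outcomes their own paragraph on follow-up, so the SAP's split could be deliberate. This stands as ambiguity. But that paragraph concerns influenza circulation, not time since vaccination, and waives nothing; if a waiver was meant, the SAP should say so. The SAP is silent rather than stating that days 0-13 count. Its counting of days from Day 15 (SAP 5.1.1.2 and 5.3) hints that later follow-up was intended, but it belongs to an optional effect-modifier or subgroup variable and sets no eligibility. SAP 5.1.1.2 also excludes people vaccinated as inpatients, which may lower the 3-7% slightly.

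**On the codes.** An rVE against admission for pneumonia or influenza is a valid quantity, so the fault is partly one of labelling, and influenza codes may sit acceptably under LRTI. That is accepted, and renaming is offered below. A reader might take 2-7 points as the expected inflation; the documents do not support this, because the upper figures need an admission share at odds with Protocol 8.1.1.

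**On refinement.** A reader might infer that the definition would be tuned with results by vaccine in view. The SAP does not say so. The gap is only that nothing rules it out.

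**On the calendar window.** Protocol 11.1 promised an SAP algorithm "to measure the intensity of influenza circulation to guide when to start and stop following for such events", and the SAP uses an assay start date and a season end instead. It is tempting to call this a departure. But the protocol delegated the choice, the SAP's end uses a test-positivity threshold, the extra 14 days are explained, and no effect can be quantified. It is not part of this point.

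**Conclusion.** The concern holds in limited form. As written, the SAP would count days 0-13 for CAP, cardio-respiratory events and the non-PCR exploratory outcomes, unlike Protocol 11.1 and its own PCR secondaries. The cost is a small dilution, a 10% rVE reading about 9.3-9.7%, which rests on assumed vaccination timing and seasonality. The CAP endpoint admits influenza without pneumonia, overlaps with hospitalised influenza and has no stated lock. Its upward effect on rVE ranges from under 1 point to 7 points depending on assumptions; values near 0.6-1.7 fit Protocol 8.1.1 better than 2.1-7.0. No effect on the composite was quantified. The two effects oppose each other for CAP, so the net bias is unknown. Nothing here touches the primary endpoint. This should be fixed before analysis but does not threaten the study's main conclusion.

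**What to change.** 1. In SAP 4.2, 4.3 and 5.1.1.2, apply the condition of at least 14 days after vaccination to every outcome, in line with Protocol 11.1.
2. In SAP Table 1, restrict J10/J11 under CAP to listed subcodes whose description specifies pneumonia, or rename the endpoint *hospitalised pneumonia or influenza*. State separately whether J10/J11 stay in the LRTI part of the composite.
3. Finalise and date the code list before any outcome is tabulated by vaccine, and delete the sentence allowing iterative refinement of CAP.

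The cost is wording and programming; no new data are needed. The 14-day condition removes about 3-7% of counted events for these outcomes under the assumptions above. Restricting J10/J11 also lowers the CAP event count, but PCR-positive admissions that meet the SAP 4.2 timing rule still count as hospitalised influenza.

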5.2 Interim / Preliminary Analysis

An interim analysis will not be performed. All recommendations will be based on the final analyses that includes all seasons.

No data will be shared beyond the immediate VSC study team as specified and approved by the KPNC IRB, namely:

- [name], PhD (Principal Investigator)
- [name] (Biostatistician)
- [name] (Data Manager)

- [name] (Project Manager)
- [name] (Project Manager)
- [name] (Project Manager)
- [name] (Senior Data Consultant)
- [name] (Senior Data Consultant)
- [name] (Senior Data Consultant)

5.3 Determination of Sample Size and Power Calculation

We calculated the least rVE that is detectable with 80% power in a 3-year study for several aims. We plan to test the null hypothesis that Flublok is not any more or less effective than the comparator, using a 2-sided test, $p<0.05$. Our allocation ratio of 1:1 implies that each year, KPNC would give Flublok Quadrivalent vaccine to 400,000 members aged 18–64 years, and SD-IIV to another 400,000 similar KPNC members.

Because the comparison group will not be unvaccinated—they are getting SD-IIV—we will be estimating and testing rVE: i.e., the percent reduction in the incidence of “breakthrough cases” (e.g., influenza episodes in vaccinees) that results from the use of Flublok Quadrivalent vaccine rather than the SD-IIV vaccines.

We may potentially conduct analyses of rVE within subgroups and periods of time defined by:

- Time-since-vaccination: number of days, counting from Day 15 after vaccination (where day 0 is the day of vaccination)
- Time-since-beginning-of-the-season
- Season: Year 1 or Year 2
- Comorbidities: Diagnostic cost groups (DxCG) risk scores from the ICD-based proprietary risk adjustment and predictive modeling system may be used. DxCG calculates projected healthcare costs for each member for the upcoming year based on demographics, diagnoses, costs, and utilization in the previous year. It may also be included as a proxy for overall health status of the individual.
- Prior healthcare utilization (e.g., number of emergency department visits or hospitalizations in prior year, outpatient visits in prior year)
- Influenza vaccine type received (or none) during the previous year

5.4 Data Review for Statistical Purposes

Since vaccinations began on September 16, 2018, we have been monitoring on a weekly basis the balance of Flublok vaccinees versus SD-IIV vaccinees with respect to service area, facility, pregnancy status, and age group. Additional demographic variables will be monitored as appropriate.

5.5 Changes in the Conduct of the Study or Planned Analyses

No significant change occurred during the conduct of the study that is not documented in a protocol amendment.

6 References List

1. US Food and Drug Administration, “Multiple Endpoints in Clinical Trials Guidance for Industry,” January 2017. Available at <https://www.fda.gov/regulatory-information/search-fda-guidance-documents/multiple-endpoints-clinical-trials-guidance-industry>. Accessed 29 Jan 2020.

List of Tables

Table 1. Preliminary ICD-10 codes for identifying cardio-respiratory outcomes.....	23
--	----

Table 1. Preliminary ICD-10 codes for identifying cardio-respiratory outcomes

Outcome	ICD-10 Code	Description
Community-acquired pneumonia (CAP)	J10.*	Influenza due to other identified influenza virus
	J11.*	Influenza due to unidentified influenza virus
	J12.*	Viral pneumonia, not elsewhere classified
	J13	Pneumonia due to Streptococcus pneumoniae
	J14	Pneumonia due to Hemophilus influenzae
	J15.*	Bacterial pneumonia, not elsewhere classified
	J16.*	Pneumonia due to other infectious organisms, not elsewhere classified
	J17	Pneumonia in diseases classified elsewhere
	J18.* (except for J18.2: Hypostatic pneumonia, unspecified organism)	Pneumonia, unspecified organism
Acute myocardial infarction	I21.x	Acute myocardial infarction
Heart failure	I50.x	Heart failure
Lower respiratory tract infections (LRTI)	(All codes from CAP above)	
	J20.x	Acute bronchitis
	J40	Bronchitis, not specified as acute or chronic
	J44.0	Chronic obstructive pulmonary disease with acute lower respiratory infection
Stroke	I60.x	Nontraumatic subarachnoid hemorrhage
	I61.x	Nontraumatic intracerebral hemorrhage
	I63.x	Cerebral infarction
Atrial fibrillation	I48.1	Persistent atrial fibrillation

Note: “.x” indicates that all subcodes listed under the main code may be used.

Table 2. Proposed ICD-10 codes for identifying pre-existing conditions

Pre-existing Condition	Sub-category	ICD-10 Code	Description
Cardiovascular preexisting conditions composite	Myocardial infarction, coronary heart disease	I20.*	Angina pectoris
		I21.*	Acute myocardial infarction
		I22.*	Subsequent myocardial infarction
		I23.*	Certain current complications following acute myocardial infarction
		I24*	Other acute ischaemic heart diseases
		I25*	Chronic ischaemic heart disease
	Cerebrovascular accident	I60.*	Subarachnoid haemorrhage
		I61.*	Intracerebral haemorrhage
		I62.*	Other nontraumatic intracranial haemorrhage
		I63.*	Cerebral infarction
		I64	Stroke, not specified as haemorrhage or infarction
		I65.*	Occlusion and stenosis of precerebral arteries, not resulting in cerebral infarction
		I66.*	Occlusion and stenosis of cerebral arteries, not resulting in cerebral infarction
		I67.*	Other cerebrovascular diseases
		I68.*	Cerebrovascular disorders in diseases classified elsewhere
		I69.*	Sequelae of cerebrovascular disease
	Atrial fibrillation	I48.*	Atrial fibrillation and flutter
	Arrhythmias	I49.*	Other cardiac arrhythmias
		I47.*	Paroxysmal tachycardia
		I44.*	Atrioventricular and left bundle-branch block
		I45.*	Other conduction disorders

Valvular heart disease	I05.*	Rheumatic mitral valve diseases
	I06.*	Rheumatic aortic valve diseases
	I07.*	Rheumatic tricuspid valve diseases
	I08.*	Multiple valve diseases
	I09.1	Rheumatic diseases of endocardium, valve unspecified
	I09.8	Rheumatic disease of pulmonary valve
	I34.*	Nonrheumatic mitral valve disorders
	I35.*	Nonrheumatic aortic valve disorders
	I36.*	Nonrheumatic tricuspid valve disorders
	I37.*	Pulmonary valve disorders
	I38	Endocarditis, valve unspecified
	I39.*	Endocarditis and heart valve disorders in diseases classified elsewhere
	I50.*	Heart failure
Chronic/congestive heart failure	I09.9	Rheumatic heart failure
	I11.0	Hypertensive heart disease with (congestive) heart failure
	I13.0	Hypertensive heart and renal disease with (congestive) heart failure
	I13.02	Hypertensive heart and renal disease with both (congestive) heart failure and renal failure
	Z95.*	Presence of cardiac and vascular implants and grafts
CABG/valvuloplasty/angioplasty/stents/pacemaker/cardioverter	T82.*	Complications of cardiac and vascular prosthetic devices, implants and grafts
Congenital heart defects	Q20.*	Congenital malformations of cardiac chambers and connections
	Q21.*	Congenital malformations of cardiac septa
	Q22.*	Congenital malformations of pulmonary and tricuspid valves
	Q23.*	Congenital malformations of aortic and mitral valves
	Q24.*	Other congenital malformations of heart
	Q25.*	Congenital malformations of great arteries

		Q26.*	Congenital malformations of great veins
		Q27.*	Other congenital malformations of peripheral vascular system
		Q28.*	Other congenital malformations of circulatory system
Respiratory preexisting conditions composite	Hypertensive disease	I10.*	Essential (primary) hypertension
		I11.*	Hypertensive heart disease
		I12.*	Hypertensive chronic kidney disease
		I13.*	Hypertensive heart and chronic kidney disease
		I15.*	Secondary hypertension
		I16.*	Hypertensive crisis
Respiratory preexisting conditions composite	Chronic obstructive pulmonary disease	J40.*	Bronchitis, not specified as acute or chronic
		J41.*	Simple and mucopurulent chronic bronchitis
		J42.*	Unspecified chronic bronchitis
		J43.*	Emphysema
		J44.*	Other chronic obstructive pulmonary disease
	Pulmonary hypertension	I27.*	Other pulmonary heart diseases
		I28.*	Other diseases of pulmonary vessels
		I26.*	Pulmonary embolism
Obesity	Based on calculated height/weight $BMI \geq 30$ and/or presence of ICD-10 codes	E66.0	Obesity due to excess calories
		E66.1	Drug-induced obesity
		E66.2	Extreme obesity with alveolar hypoventilation
		E66.8	Other obesity
		E66.9	Obesity, unspecified
Diabetes	N/A	E10.*	Type 1 diabetes mellitus
		E11.*	Type 2 diabetes mellitus
		E12.*	Malnutrition-related diabetes mellitus
		E13.*	Other specified diabetes mellitus
		E14.*	Unspecified diabetes mellitus

Note: “.x” indicates that all subcodes listed under the main code may be used.

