2.2 Secondary Objectives

Among all adults 50–64 years who receive either Flublok Quadrivalent or SD-IIV during the 2018–2019, 2019–2020, and/or 2020–2021 influenza seasons, we will estimate the rVE of Flublok Quadrivalent vaccine versus SD-IIV against the following outcomes:

- PCR-confirmed hospitalized influenza
- Hospitalized community-acquired pneumonia (CAP) (we will only include primary diagnoses for this outcome)
- Hospitalized cardio-respiratory events combined (e.g., CAP, other lower respiratory tract infections [LRTI], acute myocardial infarction, congestive heart failure, stroke, atrial fibrillation) (we will only include primary diagnoses for this outcome)
- All PCR-confirmed influenza A
- All PCR-confirmed influenza B

For these 5 secondary objectives, adjustment for multiplicity will be applied.

Sub-analyses of *primary* outcome in sub-groups defined by pre-existing conditions (listed below) will also be conducted among adults 50–64 years. Additionally, sub-analyses of *secondary*

outcomes of sub-groups defined by pre-existing conditions will be conducted as feasible among adults 50–64 years.

“Pre-existing” will be defined as history of a condition in the 3 years prior to vaccination date.

- i. **Cardiovascular preexisting conditions composite, which may include:** myocardial infarction, cerebrovascular accident, atrial fibrillation, arrhythmias, coronary artery disease, valvular heart disease/valvuloplasty, chronic/congestive heart failure and/or congenital heart defects, CABG, angioplasty/stents, cardioversion, pacemaker, implantable cardioverter defibrillator, LVAD, heart transplant, hypertensive disease
- ii. **Respiratory preexisting conditions composite, which may include:** COPD and/or pulmonary HTN
- iii. **Cardiorespiratory preexisting conditions composite:** combined pre-existing conditions (a) and (b) above
- iv. **Obesity:** based on available height/weight data for a calculated BMI ≥ 30 or an obesity diagnosis (e.g., ICD-10 E66.9)
- v. **Diabetes:** based on a diagnosis of diabetes

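### The heart-failure outcome in SAP Table 1 is I50.x only, while Table 2 also describes I09.9, I11.0, I13.0 and I13.02 as heart failure; admissions with those primary codes would not count.

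*SAP*

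**What the plan says.** SAP 2.2 lists the hospitalized cardio-respiratory composite among five secondary outcomes in adults aged 50–64. Its examples include "acute myocardial infarction, congestive heart failure, stroke, atrial fibrillation", and the restriction attached to it is "we will only include primary diagnoses for this outcome". SAP 4.2 tests the five outcomes by the Holm method, with the smallest p-value compared with 0.0100.

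For identifying cardio-respiratory events, SAP 4.2 says "we will start with preliminary list of ICD-10 codes that has been previously used by KPNC" and points to Table 1, titled "Preliminary ICD-10 codes for identifying cardio-respiratory outcomes". The heart-failure row of Table 1 has one entry, I50.x.

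SAP Table 2 gives codes for pre-existing conditions. For chronic/congestive heart failure it lists I50.* and four more codes:
- I11.0, which the table describes as "Hypertensive heart disease with (congestive) heart failure"
- I13.0, the matching entry where the kidney is involved as well as the heart
- I13.02, whose description names failure of both organs
- I09.9, which the table describes as "Rheumatic heart failure"

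Neither document says why the outcome list is shorter than the history list.

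**The concern.** The four extra codes are described as heart failure itself, not as a risk factor or a late consequence of it. The same condition is therefore recognised as history under five code entries and as an outcome under one.

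The primary-diagnosis rule gives the gap its effect. If an admission for heart failure carries I11.0 or I13.0 in first position and I50 in second, the first code is not in Table 1 and the second is in the wrong position, so nothing is counted. At stake are the number of events in a Holm-tested endpoint and the match between its stated content and what it measures. Three of the four codes are hypertensive codes, and SAP 2.2 includes hypertensive disease in the cardiovascular pre-existing-conditions composite. Uncounted admissions would therefore tend to fall in a subgroup that the SAP plans to analyse.

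**Working it through.** **Code comparison.**
- Table 1, heart failure: {I50.x}
- Table 2, heart failure: {I50.*, I09.9, I11.0, I13.0, I13.02}
- Difference: {I09.9, I11.0, I13.0, I13.02}

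The other Table 1 rows cover J10–J18 (except J18.2), J20, J40, J44.0, I21, I60, I61, I63 and I48.1. None of the four missing codes appears there, so no other component picks these admissions up.

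**Diagnosis position.** The restriction to primary diagnoses is in SAP 2.2. SAP 4.2 does not repeat it but says nothing against it. Under SAP 2.2, a secondary I50 code cannot make the admission an event.

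**Room for change.** SAP 4.2 calls the list preliminary for both pneumonia and cardio-respiratory events. The sentence allowing iterative refinement during analysis names community-acquired pneumonia only.

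**Size.** The documents do not give the share of events with these primary codes, so only a range under assumption is possible. The nearest powered outcome is CVD hospitalization, December–March, ages 50–64 (protocol power tables, rows 43–48).

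Inputs: n = 519,699 per arm and comparator proportion p = 0.00620, or 519,699 × 0.00620 = 3,222 comparator events.

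Formula, with p̄ = p(1 + RR)/2:

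z = p(1 − RR) / √[2p̄(1 − p̄)/n], power ≈ Φ(z − 1.960) at 2-sided alpha 0.05, or Φ(z − 2.576) at 0.01.

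The protocol's own figures come first:
- RR 0.90: z = 4.130, power = Φ(2.170) = 0.985 (stated 0.99)
- RR 0.95: z = 2.039, power = Φ(0.079) = 0.531 (stated 0.53)

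The likelihood-ratio chi-square calculation named in the protocol gives the same values, so the method reproduces the plan.

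Now suppose that a fraction f of all composite events is missed equally in both arms. Then p becomes 0.00620(1 − f), and z shrinks by about √(1 − f). For rVE 8% (RR 0.92), p(1 − RR) = 0.000496, p̄ = 0.005952 and z = 0.000496/0.0001509 = 3.287 at f = 0. At f = 0.30, z ≈ 3.287 × √0.70 = 2.750 and power = Φ(0.790) = 0.785.

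| f (assumed) | rVE 8%, alpha 0.05 | rVE 8%, alpha 0.01 | rVE 10%, alpha 0.05 | rVE 5%, alpha 0.05 |
|---|---|---|---|---|
| 0 | 0.908 | 0.762 | 0.985 | 0.531 |
| 5% | 0.893 | 0.735 | 0.981 | 0.511 |
| 10% | 0.877 | 0.706 | 0.975 | 0.489 |
| 20% | 0.836 | 0.642 | 0.958 | 0.445 |
| 30% | 0.785 | 0.568 | 0.932 | 0.399 |

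The alpha 0.01 column is the first Holm step. The least rVE detectable with 80% power at alpha 0.05 moves from 6.8% (f = 0) to 7.0%, 7.2%, 7.6% and 8.2%.

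**The case against.** A reader might infer that Table 1 is wrong by the SAP's own definition of heart failure. The documents do not support that. Table 2 defines history and Table 1 defines outcomes, and neither claims to govern the other. Table 1 is also narrower for other shared conditions: I21 against I20–I25 for myocardial infarction and coronary disease; I60, I61 and I63 against I60–I69 for stroke; I48.1 against I48.* for atrial fibrillation. A broad history list beside a narrow acute-event list is a common choice, and Table 1 is expressly a starting list. What remains is that the narrower heart-failure row is unexplained and that, unlike chronic ischaemic disease or stroke sequelae, the omitted codes are described as the condition itself.

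A reader might also infer a large loss of events. That depends on how coders order the hypertensive codes and I50, which the documents do not say. They show only that such an admission would not count if it occurred. A 30% loss would require admissions under the omitted codes alone to make up 30% of a composite that also holds pneumonia, other lower respiratory infection, infarction, stroke and atrial fibrillation; nothing supports that figure. The stand-in row is imperfect too. It is labelled CVD, covers December–March, and does not state its codes, whereas the SAP composite adds respiratory events and runs from about October until 14 days after the season ends. If 0.00620 already rests on I50 alone, the stated power already reflects the omission. These points stand, and they make the power figures illustrative.

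Finally, a reader might infer a biased vaccine comparison. One list applies to both groups, and nothing suggests that coding order depends on the vaccine received.

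**Conclusion.** The point holds as an unexplained gap in an outcome definition. As written, admissions with primary code I09.9, I11.0, I13.0 or I13.02 are left out of an endpoint that names congestive heart failure. The conclusion rests on the primary-diagnosis restriction in SAP 2.2 and on Table 1 being used as it stands.

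The consequence is fewer events and a narrower endpoint than its name implies. The size is unknown. Under the assumed losses, the effect is small at 5% (about 1.5 percentage points of power at rVE 8%, alpha 0.05) and material only if the loss is large (about 12 points at 30%). rVE 8% is not one of the protocol's scenarios; at its 10% scenario, power stays at 0.93 or above throughout at alpha 0.05. The matter concerns one component of one secondary endpoint. The primary PCR-confirmed endpoint is unaffected. It is a cheap improvement, not a threat to the study's main conclusion.

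**What to change.** Before analysis, extend the heart-failure row of Table 1 to the heart-failure codes already in Table 2: I50.x, I09.9, I11.0, I13.0 and the combined heart-and-renal heart-failure code. Table 2 gives that last code as I13.02, which by its form is a subcode of I13.0; check code and description against the code book in use before fixing the list. Keep the I50-only definition as a sensitivity analysis, and report how many events the added codes contribute in each vaccine group.

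If the narrower set is intended, say so in the SAP with the reason. Either way, settle the list before outcomes are analysed by vaccine, because this endpoint is tested under Holm.

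The cost is one table row and one sensitivity analysis. Protocol 8.2.1 already names discharge ICD-10 codes as the source, so no new kind of data is needed. The small downside is a departure from the list KPNC has used before, and the added events could dilute the composite if the vaccine effect on them is weaker. The sensitivity analysis addresses both.
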